10.3.6.1.4. SEITQ = Self-efficacy about Insulin Therapy
Questionnaire (SEITQ) 35

10.3.6.2. Subgroup Analyses 35

10.3.7. Interim Analyses 36

11. References 37

12. Appendices 39

List of Tables

Table	Page
Table IOQR.1. Schedule of Activities for Prospective Cohorts	11
Table IOQR.2. Objectives and Endpoints.....	15

List of Figures

Figure

Page

Figure IOQR.1. Illustration of study design for Pragmatic Study F3Z-GH-IOQR..... 18

List of Appendices

Appendix		Page
Appendix 1.	Abbreviations and Definitions.....	40
Appendix 2.	World Health Organization Classification of Diabetes	43
Appendix 3.	Study Governance Considerations.....	44

1. Synopsis

Title of Study:

Comparison Between Basal Insulin Analog and Insulin Analog Mid Mixture As Starter Insulin for Chinese Patients With Type 2 Diabetes Mellitus (CLASSIC Study)

Rationale:

The purpose of Study is to compare basal insulin analog once daily(QD) and insulin analog mid mixture twice daily (BID) as starter insulin regimen in Chinese patients with type 2 diabetes mellitus (T2DM) who have inadequate glycemc control with oral antihyperglycemic medications (OAMs) in real world settings.

Objective(s)/Endpoints:

Objectives	Endpoints
Primary	
1. To compare change in HbA1c from baseline to 24 weeks between insulin analog mid mixture BID and basal insulin analog QD treatments	1. The change in HbA1c from baseline to 24 weeks
Secondary	
2. To compare change in HbA1c from baseline to 48 weeks between insulin analog mid mixture BID and basal insulin analog QD treatments	2. The change in HbA1c from baseline to 48 weeks
3. To compare the proportion of patients who achieve HbA1c <7% at 24 and 48 weeks between insulin analog mid mixture BID and basal insulin analog QD treatments	3. Proportion of patients who achieve HbA1c <7% at 24 and 48 weeks
4. To compare the change in venous FPG from baseline to 24 and 48 weeks between insulin analog mid mixture BID and basal insulin analog QD treatments	4. Venous FPG change from baseline at 24 and 48 weeks
5. To compare the change in FSBG-based FBG and PPG from baseline to 24 and 48 weeks between insulin analog mid mixture BID and basal insulin analog QD treatments	5.FSBG-based FBG, PPG change from baseline at 24 and 48 weeks
6. To compare the daily insulin dose at 24 and 48 weeks between insulin analog mid mixture BID and basal insulin analog QD treatments	6. Daily insulin dose at 24 and 48 weeks
7. To compare the change in body weight from baseline to 24 and 48 weeks between insulin analog mid mixture BID and basal insulin analog QD treatments	7. Body weight change from baseline at 24 and 48 weeks
8. To compare the severe, nocturnal and total hypoglycemia incidences and rates during the 24-week and 48-week treatment period between insulin analog mid mixture BID and basal insulin analog QD treatments	8. The severe, nocturnal and total hypoglycemia incidences and rates during the 24-week and 48-week treatment period

Objectives	Endpoints

9. To compare time to insulin treatment change between insulin analog mid mixture BID and basal insulin analog QD treatments
	
9. Time to insulin treatment change: Defined as time to any of: insulin treatment discontinuation, switch, intensification or reduction in frequency
 
Discontinuation: Defined as stopping insulin treatment for 30 days or more.
 
Switch: Defined as stop the initial insulin therapy and started another insulin therapy of different class.
 
Intensification: Defined as any of the following: adding meal time insulin in basal insulin analog QD group; changing from BID to TID in insulin analog mid mixture BID group
 
Reduction in frequency: Defined as any of the following: changing from BID to QD; changing from TID to BID or QD

10. To compare the proportion of patients who achieve the HbA1c <7% without switching and discontinuing study insulin, and without using rescue therapy between insulin analog mid mixture BID and basal insulin analog QD treatments
	
10. Proportion of patients who achieve the HbA1c <7% without switching and discontinuing study insulin, and without using rescue therapy

11. To compare the patients-reported self-efficacy related to insulin therapy as assessed using SEITQ between insulin analog mid mixture BID and basal insulin analog QD treatments
	
11. The change in SEITQ score form baseline at 48 weeks

Abbreviations: BID = twice daily; FBG = fasting blood glucose; FPG = fasting plasma glucose; FSBG =finger stick blood glucose; HbA1c = hemoglobin A1c; PPG = post prandial glucose; QD = once daily; SEITQ = Self-efficacy about Insulin Therapy Questionnaire; TID = three times a day.

Summary of Study Design:

Study F3Z-GH-IOQR (IOQR) is a multicenter, open-label, randomized, 48-week, parallel, 2-arm pragmatic trial comparing the effectiveness of basal insulin analog QD and insulin analog mid mixture BID treatments in real world setting in adult Chinese patients (≥18 and ≤80 years) with T2DM who have failed to achieve adequate glycemic control with OAMs (hemoglobin A1c [HbA1c] ≥7.5%)

Treatment Arms and Duration:

There are 2 arms in this 48 week study: basal insulin analog QD arm and insulin analog mid mixture BID arm

Number of Patients:

Approximately 830 participants will be randomized 1:1 into the 2 treatment groups such that there will be approximately 664 evaluable participants for primary analyses at Week 24.

Statistical Analysis:

General Considerations: Both efficacy and safety analyses will be performed on randomized patients.

All tests of treatment effects will be conducted at a 2-sided alpha level of 0.05, unless otherwise stated.

The baseline value for measurements will be defined as the last non-missing observation on or before the randomization visit. If no data are available, the baseline value will be treated as missing.

For continuous measures, summary statistics will include at least number of patients with data, mean, standard deviation (SD), median, minimum, and maximum. For categorical measures, summary statistics will include at least number of patients with data, frequency counts, and percentages. For comparisons based on analysis models, the differences will be reported using least squares (LS) means, along with 95% confidence intervals (CIs) and p-value. Sometimes, treatment-wise comparison on the summary statistics may be performed and p-values provided, and such p-values should be viewed as a descriptive measure only. Unless specified otherwise, a two-sample t-test will be used for continuous measurements and Fisher's exact test will be used for categorical measurements.

Primary Analysis: Missing measurements will not be imputed as HbA1c will be only measured once post-baseline at Week 24. In addition to common summary statistics for the change from baseline data, the comparison between 2 treatment arms will be conducted using an analysis of covariate (ANCOVA) model, with change from baseline in HbA1c as response, treatment as fixed effect and baseline HbA1c as a covariate. The 95% CI of LS means difference (insulin analog mid mixture BID – basal insulin analog QD) will be used to make conclusions for the comparison.

Secondary Analyses: For change from baseline in venous fasting plasma glucose (FPG), finger stick blood glucose (FSBG)-based fasting blood glucose (FBG), post prandial glucose (PPG) and blood glucose (BG) excursion, the analyses model will be similar to the primary analyses model, except that the comparison will be based on the treatment contrast p-value from the ANCOVA model.

For percentages of patients reaching treatment goals (<7%) at Week 24 and Week 48, no missing data will be imputed. Count and percentages of patients reaching treatment goals will be summarized, and also be analyzed by a logistic regression model, with logit link function, treatment as fixed effect and baseline HbA1c as continuous covariate.

Insulin dose at each visit will be descriptively summarized by treatment groups by total daily dose (IU and IU/kg).

Safety: The incidence rate of case report form (CRF) collected severe, nocturnal and total hypoglycemic events will be summarized by visit and for the overall study duration. Pairwise comparison between treatment arms will be performed by Fisher's exact test. The overall yearly rates (events/patient/year) of those hypoglycemic events, calculated as, for each patient, the number of episodes times 365.25 and then divided by the patient's treatment duration, will be summarized, and analyzed by a negative-binomial regression model with treatment as fixed effects and log of (patient's treatment duration/365.25) as an offset variable.

Other Analyses: For the medial resource utilization and patient-reported outcome measurements summary statistics will be provided and comparison will be performed by appropriate general test.

Subgroup analysis will be performed for baseline HbA1c, baseline morning PPG, BG excursion, gender, and persistence levels in 2 treatment groups.

2. Schedule of Activities

Table IOQR.1. Schedule of Activities for Prospective Cohorts

eCRF Visit No.:	1	2	3	4	5	6	ET ^a
Week of treatment	0	4	12	24	36	48	ET
Visit Window (days)	–	±7	±7	±7	±14	±14	±14
Informed consent (before procedures/tests)	X						
Demographics	X						
Weight	X	X	X	X	X	X	X
Height	X						
Local urine pregnancy test ^b	X						
Duration of diabetes	X						
Anti-hyperglycemic medications(Non-insulin)	X	X	X	X	X	X	X
Insulin treatment ^c	X	X	X	X	X	X	X
Insulin dose ^d	X	X	X	X	X	X	X
Preexisting conditions/Adverse events ^e	X	X	X	X	X	X	X
Severe, nocturnal and total hypoglycemia events ^f	X	X	X	X	X	X	X
Other categories of hypoglycemia events (if available) ^g	X	X	X	X	X	X	X
HbA1c	X ^h			X ⁱ		X ⁱ	X ⁱ
Venous FPG ^j	X			X		X	X
2-point FSBG (pre-breakfast FBG and post-breakfast PPG) ^k	X			X		X	X
Randomization	X						
SEITQ	X			X		X	X
ITSQ				X		X	X
Healthcare resource utilization	X		X	X	X	X	X
Patient training	X						
Dispense study diary and instruct to use	X	X	X	X	X		
Review study diary		X	X	X	X	X	X

Abbreviations: eCRF = electronic case report form; ET = early termination; FBG = fasting blood glucose; FPG = fasting plasma glucose; FSBG = finger stick blood glucose; HbA1c = hemoglobin A1c; ITSQ = Insulin Treatment Satisfaction Questionnaire; No. = number; PPG = post prandial glucose; SEITQ = Self-efficacy about Insulin Therapy Questionnaire.

- a Early termination (ET) visit is conducted within 14 days after the decision of discontinuation. At ET visit, fasting laboratory samples will be collected if possible.
- b A urine pregnancy test will be performed locally only for women of childbearing potential.
- c The current insulin treatment regimen, insulin treatment pattern change from last visit including insulin discontinuation, switch, intensification and reduction in frequency, and reason for insulin treatment pattern change will be recorded
- d For Visit 1, prescribed daily insulin dose by the physician will be recorded. For the following visits, actual daily insulin dose of day prior to the visit will be recorded. If the insulin treatment is temporarily suspended or discontinued before the visit, the actual daily insulin dose of the day in which the patient received his/her last insulin treatment will be recorded.
- e After the informed consent form (ICF) is signed, study site personnel will record the occurrence and nature of each patient's preexisting conditions. In addition, site personnel will record any change in the condition(s) and any new conditions as AEs.
- f Severe, nocturnal and total hypoglycemia events will be collected and analyzed as secondary endpoints.
- g Other categories of hypoglycemia (documented symptomatic, asymptomatic, unspecified, probable symptomatic and relative hypoglycemia) events will be collected if available and analyzed as exploratory objectives
- h Blood draw is not required for patients who already have measurement prior to study entry (value within 12 weeks).
- i HbA1c will be drawn locally +/- 4 weeks of visit date
- j Venous FPG will be drawn locally after a fast of at least 8 hours without eating, drinking (except for water) or performing any significant physical activity +/- 2 weeks of visit date. Missing venous FPG measurement will not be considered as a protocol violation.
- k Two-point FSBG [pre-breakfast (fasting) FBG and post-breakfast (approximately 2 hours after breakfast) PPG] should be measured on one day within 1 to 2 weeks before or at Visit 1 (Week 0), Visit 4 (Week 24), Visit 6 (Week 48) or the ET visit (if possible).

3. Introduction

The International Diabetes Federation (IDF) reports that the number of people with type 2 diabetes mellitus (T2DM) is going up in every country, particularly in Asian countries such as China due to multiple contributing factors, including diet, genes, and lifestyle (Hu 2011). By 2035, the prevalence of diabetes is estimated to be 592 million globally, with an estimation of 143 million in China alone (IDF Diabetes Atlas 2013). A recent national survey in China estimated that about 9.7% of Chinese adults might have had diabetes, suggesting that China has the largest population of individuals with type 2 diabetes in the world (Yang et al. 2010).

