3.3. Benefit/Risk Assessment

More detailed information about the known and expected benefits and risks of study insulin treatments may be found in the package inserts of these insulin products.

4. Objectives and Endpoints

Table IOQR.2 shows the objectives and endpoints of the study.

Table IOQR.2. Objectives and Endpoints

Objectives	Endpoints
Primary	
1. To compare change in HbA1c from baseline to 24 weeks between insulin analog mid mixture BID and basal insulin analog QD treatments	1. The change in HbA1c from baseline to 24 weeks
Secondary	
2. To compare change in HbA1c from baseline to 48 weeks between insulin analog mid mixture BID and basal insulin analog QD treatments	2. The change in HbA1c from baseline to 48 weeks
3. To compare the proportion of patients who achieve HbA1c <7% at 24 and 48 weeks between insulin analog mid mixture BID and basal insulin analog QD treatments	3. Proportion of patients who achieve HbA1c <7% at 24 and 48 weeks
4. To compare the change in venous FPG from baseline to 24 and 48 weeks between insulin analog mid mixture BID and basal insulin analog QD treatments	4. Venous FPG change from baseline at 24 and 48 weeks
5. To compare the change in FSBG-based FBG and PPG from baseline to 24 and 48 weeks between insulin analog mid mixture BID and basal insulin analog QD treatments	5. FSBG-based FBG, PPG change from baseline at 24 and 48 weeks
6. To compare the daily insulin dose at 24 and 48 weeks between insulin analog mid mixture BID and basal insulin analog QD treatments	6. Daily insulin dose at 24 and 48 weeks
7. To compare the change in body weight from baseline to 24 and 48 weeks between insulin analog mid mixture BID and basal insulin analog QD treatments	7. Body weight change from baseline at 24 and 48 weeks
8. To compare the severe, nocturnal and total hypoglycemia incidences and rates during the 24-week and 48-week treatment period between insulin analog mid mixture BID and basal insulin analog QD treatments	8. The severe, nocturnal and total hypoglycemia incidences and rates during the 24-week and 48-week treatment period

Objectives and Endpoints

Objectives	Endpoints

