3. STUDY OBJECTIVES AND ENDPOINTS

The objectives and endpoints of the study shows below:

Objectives	Endpoints
Primary	
1. To compare change in HbA1c from baseline to 24 weeks between insulin analog mid mixture BID and basal insulin analog QD treatments	1. The change in HbA1c from baseline to 24 weeks
Secondary	
2. To compare change in HbA1c from baseline to 48 weeks between insulin analog mid mixture BID and basal insulin analog QD treatments	2. The change in HbA1c from baseline to 48 weeks
3. To compare the proportion of patients who achieve HbA1c <7% at 24 and 48 weeks between insulin analog mid mixture BID and basal insulin analog QD treatments	3. Proportion of patients who achieve HbA1c <7% at 24 and 48 weeks
4. To compare the change in venous FPG from baseline to 24 and 48 weeks between insulin analog mid mixture BID and basal insulin analog QD treatments	4. Venous FPG change from baseline at 24 and 48 weeks
5. To compare the change in FSBG-based FBG and PPG from baseline to 24 and 48 weeks between insulin analog mid mixture BID and basal insulin analog QD treatments	5.FSBG-based FBG, PPG change from baseline at 24 and 48 weeks
6. To compare the daily insulin dose at 24 and 48 weeks between insulin analog mid mixture BID and	6. Daily insulin dose at 24 and 48 weeks

basal insulin analog QD treatments	
7. To compare the change in body weight from baseline to 24 and 48 weeks between insulin analog mid mixture BID and basal insulin analog QD treatments	7. Body weight change from baseline at 24 and 48 weeks
8. To compare the severe, nocturnal and total hypoglycemia incidences and rates during the 24-week and 48-week treatment period between insulin analog mid mixture BID and basal insulin analog QD treatments	8. The severe, nocturnal and total hypoglycemia incidences and rates during the 24-week and 48-week treatment period

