8.2.2. Secondary Analyses

Missing efficacy values which are HbA1c, FPG, FSBG-based FBG, PPG, BG excursion daily insulin, body weight, SEITQ score will do LOCF. Those missing values will be the last non-missing post-baseline observation up to date of missing values of measurement.

All secondary efficacy endpoints will be listed separately for each subject at each planned visit.

1. For change from baseline in HbA1c at Week 48, the analyses model will be similar to the primary analyses model, and the sensitivity analyses will also be performed.

Also, a mixed-model repeated measures (MMRM) model will be employed to analyze the HbA1c change from baseline at Week 24 and Week 48. This MMRM model will have all post-baseline HbA1c as responses, baseline HbA1c as a continuous covariate, treatment group, Visits (Week 24 or Visit 48), and treatment by visit interaction as fixed effects and patient as a random effect. An unstructured covariance structure will be used to model the correlation within subjects. In case of failure of convergence using unstructured covariance structure, the first-order autoregressive [AR(1)] covariance structure will be used. Missing data will be assumed to be missing at random and therefore maintained as missing. The difference between each of treatment will be assessed by the least-squares means (LSM) difference at Week 24 and Week 48 (alpha=0.05, 2-sided).

A plot of least-squares means for change from baseline by visit for each treatment will be used to display the results of this endpoint.

As sensitivity analyses, the endpoint analyses will be repeated by censoring all efficacy data after patients changed the randomized treatment regimen at Week 48, Ancova analyses for row data and LOCF data at Week 48 separately.

2. For change from baseline in venous FPG, FSBG-based FBG, PPG, BG excursion and bodyweight at Week 24 and Week 48, the analyses will be done similarly to the primary analyses model (ANCOVA for Week 24 and Week 48, and MMRM for Week 24 and Week 48), except for comparison will be based on the treatment contrast p-value from the corresponding analyses model. The sensitivity analyses will also be performed.

Plots of least-squares means for change from baseline by visit for each treatment will be used to display the results of endpoints.

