As sensitivity analyses, the endpoint analyses will be repeated by censoring all efficacy data after patients changed the randomized treatment regimen at Week 24 and Week 48, Ancova analyses for row data and LOCF data at Week 24 and Week 48 separately.

3. For percentages of patients reaching treatment goals (<7%) at Week 24 and Week 48, no missing data will be imputed. Count and percentages of patients reaching treatment goals will be summarized (when calculating percentages, the denominator will be the patients with non-missing HbA1c data at Week 24 or Week 48), and also be analyzed by a logistic regression model, with logit link function, treatment as fixed effect and baseline HbA1c as continuous covariate. Adjusted odds ratio, 95% CI and P-value will be presented. Related plot will be reported.

Plots of percentages of patients reaching treatment goals by visit for each treatment will be used to display the results of endpoints.

As sensitivity analyses, the endpoint analyses will be repeated by censoring all efficacy data after patients changed the randomized treatment regimen at Week 24 and Week 48, Ancova analyses for row data and LOCF data at Week 24 and Week 48 separately.

4. Same analyses strategy (refer to above 3) will be used for the composite endpoint of patients reaching treatment goals (<7%) and did not switch from or discontinue study treatment, and did not take rescue medication. Those patients should be without switching or discontinuing study insulin, and without using rescue therapy which will be determined by the investigator following usual standard of care between insulin analog mid mixture BID and basal insulin analog QD treatments.
5. Insulin dose at each visit will be descriptively summarized by treatment groups by total daily dose (IU and IU/kg). The descriptive statistics (n, mean, median, standard deviation, minimum, and maximum) and P-value of a two-sample t-test will be reported.
6. Time to insulin treatment change will be compared between treatment arms by a log rank test. Table and related plot will be reported. Patients who did not have any insulin treatment change up to Week 48 (or up to early discontinuation) will be considered as censored at Week 48 (or time of early discontinuation) with no event. Time to insulin treatment change: Defined as time to any of: insulin treatment

discontinuation, switch, intensification or reduction in frequency. ((date of event/censored - (date of first dose of study drug) + 1.)

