Discontinuation: Defined as stopping insulin treatment for 30 days or more.

Switch: Defined as stop the initial insulin therapy and started another insulin therapy of different class.

Intensification: Defined as any of the following: adding meal time insulin in basal insulin analog QD group; changing from BID to TID in insulin analog mid mixture BID group

Reduction in frequency: Defined as any of the following: changing from BID to QD; changing from TID to BID or QD.

Plots of time to event by weeks will be used to display the results of endpoints.

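### The Week 24 and Week 48 insulin dose averages current doses with last-taken doses from patients who are off insulin

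*Protocol*

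**What the plan says.** The objective in Protocol Section 4 (Table IOQR.2) is "To compare the daily insulin dose at 24 and 48 weeks between insulin analog mid mixture BID and basal insulin analog QD treatments". The SAP lists the endpoint in Section 3 as "6. Daily insulin dose at 24 and 48 weeks".

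Footnote d of the Schedule of Activities (Protocol Section 2) defines what goes into the dose field after Visit 1:

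- Patients on insulin: "For the following visits, actual daily insulin dose of day prior to the visit will be recorded".
- Patients off insulin: "If the insulin treatment is temporarily suspended or discontinued before the visit", then "the actual daily insulin dose of the day in which the patient received his/her last insulin treatment will be recorded". No zero is entered and no maximum age is set.

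SAP 8.2.2 item 5 states "Insulin dose at each visit will be descriptively summarized by treatment groups by total daily dose (IU and IU/kg", and adds a two-sample t-test. SAP 8.2 applies efficacy analyses to randomized patients. Item 5 does not separate patients on insulin from patients off it.

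Three further rules can bring in older doses when a visit value is missing. The opening of SAP 8.2.2 says "daily insulin, body weight, SEITQ score will do LOCF". SAP Appendix 1 uses the last record in a window that, for Week 48, opens after Visit 4. Protocol 10.3.1 takes the last non-missing post-baseline value up to the time point.

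**The concern.** The endpoint label points to the dose a patient is taking at Week 24 or Week 48. Under footnote d, a patient who stopped in the first weeks and never restarted still has a non-zero Week 48 dose. Pooled with current users, that value gives a mean answering neither of the two questions a reader is likely to bring: how much insulin do patients still using it need, and how much insulin is used on average in the arm as randomized?

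Stopping is to be expected here. Treatment after randomization is left to physician and patient (Protocol 7.1), and discontinuation is itself an outcome (Protocol 9.9.1). An arm difference in insulin dose could be partly produced, or partly hidden, by how many patients stopped and what they were last taking.

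**Working it through.** **Inputs.** The documents give no expected dose, dose SD or stopping rate, so there is no plan figure to reproduce for this endpoint. The sample size in Protocol 10.1 concerns HbA1c only and is not touched. The stopping shares and dose ratios below are assumptions, shown as a range.

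**Formulas.** Let p be the share of an arm off insulin at the visit. Let r be the mean last-taken dose of those off insulin divided by the mean current dose of those on insulin. With the user mean set to 1:

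- recorded mean (footnote d with item 5) = (1 − p) + p·r
- mean of doses actually being taken, with off insulin as zero = 1 − p
- relative excess of the recorded mean over doses actually taken = p·r / (1 − p)

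**Level within one arm: excess over doses actually taken.**

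| Share off insulin | r = 0.5 | r = 1 |
|---|---|---|
| 5% | 2.6% | 5.3% |
| 10% | 5.6% | 11.1% |
| 20% | 12.5% | 25.0% |
| 30% | 21.4% | 42.9% |

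For example, 0.10 × 1 / 0.90 = 11.1%.

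**Difference between arms.** Assume equal user doses, the same r in both arms, and 10% versus 20% off insulin.

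| Quantity | 10% off | 20% off | Difference |
|---|---|---|---|
| Users only | 1.00 | 1.00 | 0 |
| Off insulin counted as zero | 0.90 | 0.80 | 0.10 |
| Recorded, r = 1 | 0.90 + 0.10 = 1.00 | 0.80 + 0.20 = 1.00 | 0 |
| Recorded, r = 0.75 | 0.90 + 0.075 = 0.975 | 0.80 + 0.15 = 0.95 | 0.025 |
| Recorded, r = 0.5 | 0.90 + 0.05 = 0.95 | 0.80 + 0.10 = 0.90 | 0.05 |

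In general the recorded difference here is (0.20 − 0.10)(1 − r). It equals the user difference only at r = 1, and the difference in doses actually taken only at r = 0. Between those values it matches neither.

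**Age of the recorded dose.** A patient who stops soon after starting contributes a dose up to about 24 weeks old at Week 24 and about 48 weeks old at Week 48. SAP 8.5 lists a subgroup of patients who discontinued within the first 3 months (about 13 weeks). For those who have not restarted, the Week 48 dose would be at least about 48 − 13 = 35 weeks old, although they are taking none.

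**The case against.** Footnote d is an explicit, prespecified rule, and last dose taken while treated is a legitimate quantity. The analysis population is stated. Protocol 10.3.3.2 treats dose as descriptive, and SAP Section 8 calls p-values from comparisons of summary statistics descriptive only. Differential stopping will be visible elsewhere, because SAP 8.3.1 compares the proportion discontinuing by arm. A user-only comparison would condition on a post-randomization outcome.

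Most of this stands, and it rules out some stronger readings. A reader might infer that the documents contradict themselves; they do not. A reader might infer that the comparison is distorted whenever stopping differs by arm. Measured against current users, it also requires last-taken doses to differ from users' doses: with equal user doses, the recorded difference at r = 1 is 0. A reader might also blame LOCF for the mixing. A patient off insulin who attends already has a dose under footnote d, so LOCF adds older doses only for missed visits and dropouts.

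What the objection does not answer is the label. Neither document names the endpoint as last dose taken, and item 5 reports the field as the dose at each visit. The 48-week discontinuation proportion does not show how many patients in the Week 24 or Week 48 dose table were off insulin. The censoring analysis in SAP Section 8 is optional and is not listed under item 5.

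**Conclusion.** The point holds as a minor one. Followed as written, the plan reports non-zero Week 24 and Week 48 doses for patients taking no insulin, inside a mean labelled as the dose at that visit. The size cannot be determined from the documents. Under the assumed 10% versus 20% off insulin with equal user doses, the recorded arm difference is 0 at r = 1 and 5% of the user mean at r = 0.5, against 0 among users and 10% in doses actually taken.

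The effect is confined to secondary endpoint 6, which is largely descriptive. A reader might extend the concern to the primary HbA1c comparison or the sample size; neither uses the dose field.

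**What to change.** Keep footnote d as data collection and change SAP 8.2.2 item 5:

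1. Classify each patient as on or off insulin at Weeks 24 and 48 from the current-regimen field in footnote c. Classify temporary suspensions by a stated rule, for example the existing one: "Discontinuation: Defined as stopping insulin treatment for 30 days or more". Footnote c does not list short suspensions by name, so confirm that the regimen field shows them.
2. Report dose among patients on insulin at the visit, with n and percentage off insulin by arm.
3. Add a version in all randomized patients with off insulin counted as zero, so that the comparison does not rest only on patients who persisted. Patients whose status is unknown stay missing and are counted.
4. Report last dose before stopping as a separate descriptive variable.
5. Do not fill the Week 24 or Week 48 dose by LOCF or from an earlier visit in the Appendix 1 window, and state that this overrides the general rule in Protocol 10.3.1 for dose.

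The cost is SAP wording and one or two extra table rows, using fields already collected. The remaining weakness is that the user-only comparison conditions on still using insulin, so it should always appear beside the percentage off insulin and the zero-counted version.
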